IB	Investigator Brochure
ICF	Informed Consent Form

ICH	International Conference on Harmonisation
ICH GCP	International Conference on Harmonisation for Good Clinical Practice
ITT	Intention to Treat
IDSMC	Independent Data & Safety Monitoring Committee
Ig	Immunoglobulin
IMP	Investigational Medicinal Product
INR	International Normalized Ratio
irAE	Immune-related adverse events
irECI	Immune-Related Evidence of Clinical Interest
ITIM	Immunoreceptor Tyrosine-based Inhibition Motif
iTMF	Investigator Trial Master File
ITSM	Immunoreceptor Tyrosine-based Switch Motif
ISF	Investigator Site File
IV	Intravenous
L	Litre
LDH	Lactate Dehydrogenase
LFT	Liver Function Test
m	Metre
m2	Metre2
mAb	Monoclonal Antibody
mcl	Microlitre
MedDRA	Medical Dictionary for Regulatory Activities
MEL	Melanoma
mg	Milligramme
MHRA	Medicines and Healthcare Products Regulatory Agency
µM	microMolar
min	Minute
mL	Millilitre
mM	Millimolar
mmol/L	Millimoles per litre
mRECIST	modified Response Evaluation Criteria In Solid Tumours
MSD	Merck Sharp & Dohme Limited
MRI	Magnetic Resonance Imaging
MTD	Maximum tolerated dose
NCI-CTCAE	National Cancer Institute –Common Terminology Criteria for Adverse Events
NIMP	Non Investigational Medicinal Product
NICE	National Institute for Health and Clinical Excellence
nmol	Nanomoles
nmol/L	Nanomoles per litre
NSCL	Non-Small Cell Lung
NSCLC	Non-Small Cell Lung Cancer
OL	Open Label
ORR	Overall Response Rate
OR	Odds Ratio
OS	Overall Survival
OTC	Over-the-counter
PBMC	Peripheral Blood Mononuclear Cell
PD	Progressive Disease
PD	Pharmacodynamic
PFS	Progression-Free Survival
PFSR	Progression-Free Survival Rate
PI	Principal Investigator

PIS	Participant Information Sheet
PK	Pharmacokinetic
PR	Partial Response
PS	Performance Status
PT	Prothrombin Time
PT	Preferred term
QOL	Quality Of Life
Q2W	Every 2 weeks
Q3W	Every 3 weeks
Q8W	Every 8 weeks
QA	Quality Assurance
QC	Quality Control
RBC	Red Blood Cell
REC	Research Ethics Committee
RECIST	Response Evaluation Criteria In Solid Tumours
SAE	Serious Adverse Event
SAP	Statistical Analysis Plan
SAR	Serious Adverse Reaction
SD	Stable Disease
SFU	Safety Follow Up
SJS	Stevens-Johnson Syndrome
SOC	Standard of Care
SOC	System Organ Class
SmPC	Summary of Product Characteristics
SUSAR	Suspected Unexpected Serious Adverse Reaction
TAA	Tumour Associated Antigens
TACE	Trans-Arterial Chemoembolization
TB	Tuberculosis
TEN	Toxic Epidermal Necrolysis
T3	Triiodothyronine
T4	Thyroxine
TILs	Tumour-infiltrating lymphocytes
TK	Toxicokinetic

10.3	Database & Data Management	67
10.4	Data Collection	67
11.0	STUDY MANAGEMENT STRUCTURE	68
11.1	Independent Data & Safety Monitoring Committee	68
11.2	Trial Management Group	68
11.3	Early Discontinuation of the Study	68
11.4	Risk Assessment	68
11.5	Monitoring	68
11.6	Quality Control and Quality Assurance	69
11.7	Disclosure of Data and Publication	69
12.0	REFERENCES	70
	Appendices	73
	Appendix 1: Diagnostic Criteria for HCC.	73
	Appendix 2: ECOG Performance Status	73
	Appendix 3: Common Terminology Criteria for Adverse Events V4.0 (CTCAE)	74
	Appendix 4: Modified Response Evaluation Criteria in Solid Tumours (mRECIST*) Criteria for Evaluating Response in Hepatocellular Carcinoma.	74
	Appendix 5: Response Evaluation Criteria in Solid Tumours (RECIST) 1.1 Criteria for Evaluating Response in Solid Tumours	74
	SIGNATURE PAGE 1 (Chief Investigator)	75
	SIGNATURE PAGE 2 (SPONSOR)	76
	SIGNATURE PAGE 3 (principal INVESTIGATOR)	77

TRIAL SUMMARY

Title	A Phase Ib Study of Pembrolizumab following Trans-Arterial Chemoembolization in Primary Liver Carcinoma (PETAL).
Trial Phase	Ib
Clinical Indication	Primary Liver Cancer
Trial Type	Open label (OL), Single arm
Route of administration	Intravenous (IV)
Trial Blinding	None
Treatment Groups	1
Number of Trial Participants/ Sites	26-32 evaluable participants / 1-4 UK sites
Estimated duration of trial	3 Years 3 Months
Duration of Participation	Until disease progression or intolerance, withdrawal or completion of 1 year of treatment.
Study Objectives	
Primary Objective
 
 To determine the safety and tolerability of Pembrolizumab following Trans-Arterial Chemoembolization (TACE). 
Secondary Objective
 
 To evaluate the efficacy of Pembrolizumab following TACE by improving progression-free survival rates (PFSR) as measured by modified Response Evaluation Criteria In Solid Tumours (mRECIST) criteria at pre-defined 12-weekly timepoints. 
Exploratory Objective
 
 To evaluate predictive correlates of response to Pembrolizumab in hepatocellular cancer (HCC).
Study Endpoints	
Primary Endpoint
 
 To assess the safety and tolerability of Pembrolizumab using National Cancer Institute Common Terminology Criteria for Adverse Events version 4 (NCI CTCAE v4). 
Secondary Endpoints
 
 To evaluate the efficacy of Pembrolizumab following TACE using PFSR at 12 weeks (every 4 cycles) based on mRECIST criteria. 
Exploratory Endpoints
 
 To evaluate the efficacy of Pembrolizumab following TACE by improving PFSR as measured by standard Response Evaluation Criteria In Solid Tumours (RECIST) criteria v 1.1 at pre-defined 12-weekly timepoints. To identify biomarkers of immune response to Pembrolizumab using high-throughput technologies.


Summary of Main Inclusion Criteria
	
In order to be eligible for participation in this trial, the participant must:
 
 1. Be willing and able to provide written informed consent/assent for the trial. 2. Be ≥ 18 years of age on day of signing informed consent. 3. Have a diagnosis of Hepatocellular Cancer (HCC) based on AASLD criteria (Appendix 1). 4. Have at least one uni-dimensional lesion measurable by Computed Tomography (CT)-scan or Magnetic Resonance Imaging (MRI) based on mRECIST criteria. 5. Patients who received prior TACE treatment (conventional or DEB-TACE) are eligible, provided they have at least one previously untreated lesion that is measurable based on mRECIST criteria. 6. Be ineligible for surgical resection or liver transplantation. 7. Have a performance status of 0 or 1 on the Eastern Cooperative Oncology Group (ECOG) Performance Scale 8. Demonstrate adequate organ function 9. Have an overall Child-Pugh score ≤ 7 10. Female subject of childbearing potential should have a negative urine or serum pregnancy. If the urine test is positive or cannot be confirmed as negative, a serum pregnancy test will be required. 11. Women of childbearing potential must be willing to use a highly effective method of contraception as outlined in Section 6.9.2 for the course of the study through 120 days after the last dose of Investigational Medicinal Product (IMP). Note: Abstinence is acceptable if this is the usual lifestyle and preferred contraception for the subject. 12. Sexually active males must agree to use an adequate method of contraception as outlined in Section 6.9.2 starting with the first dose of IMP through 120 days after the last dose of study therapy. Note: Abstinence is acceptable if this is the usual lifestyle and preferred contraception for the subject.

Summary of Main Exclusion Criteria
	
The participant must be excluded from participating in the trial if the participant:
 
 1. Has extrahepatic metastasis. 2. Systemic anticancer treatment for HCC. 3. Has any contraindication for TACE including portosystemic shunt, hepatofugal blood flow, known severe atheromatosis. 4. Has history of bleeding within the 4 weeks preceding study enrolment. 5. Has hepatic encephalopathy. 6. Has ascites that is refractory to diuretic therapy. 7. Has documented occlusion of the hepatic artery or the main portal vein (segmental portal vein thrombosis does not represent exclusion criterion provided this does not contraindicate TACE).

	
 8. Is currently participating and receiving therapy or has participated or is participating in a study of an IMP or used an investigational device within 4 weeks of the first dose of IMP. 9. Has a diagnosis of immunodeficiency or is receiving systemic steroid therapy or any other form of immunosuppressive therapy. 10. Has a known history of active Bacillus Tuberculosis (TB) 11. Hypersensitivity to Pembrolizumab or any of its excipients. 12. Has a known additional malignancy that is progressing or requires active treatment. Exceptions include basal cell carcinoma of the skin or squamous cell carcinoma of the skin that has undergone potentially curative therapy or in situ cervical cancer. 13. Has active autoimmune disease that has required systemic treatment in the past 2 years (i.e. with use of disease modifying agents, corticosteroids or immunosuppressive drugs). Replacement therapy (eg. thyroxine, insulin, or physiologic corticosteroid replacement therapy for adrenal or pituitary insufficiency, etc.) is not considered a form of systemic treatment. 14. Has known history of, or any evidence of active, non-infectious pneumonitis. 15. Has an active infection requiring systemic therapy. Exceptions relating to Hepatitis B and C virus infection are documented in Section 5.3.1, Table 5. 16. Has a history or current evidence of any condition, therapy, or laboratory abnormality that might confound the results of the trial, interfere with the subject's participation for the full duration of the trial, or is not in the best interest of the subject to participate, in the opinion of the treating Principal Investigator (PI). 17. Has known psychiatric or substance abuse disorders that would interfere with cooperation with the requirements of the trial. 18. Is pregnant or breastfeeding, or expecting to conceive or father children within the projected duration of the trial, starting with the screening visit through to 120 days after the last dose of IMP. 19. Has received prior therapy with an anti-PD-1, anti-PD-L1, or anti-PD-L2 agent. 20. Has a known history of Human Immunodeficiency Virus (HIV; HIV 1/2 antibodies). 21. Has received a live vaccine within 30 days of first dose of IMP administration. 
Note: Seasonal influenza vaccines for injection are generally inactivated flu vaccines and are allowed; however intranasal influenza vaccines (e.g., Flu-Mist®) are live attenuated vaccines, and are not allowed.

Treatment / Main Study Procedures	TACE. Trans-arterial chemoembolization will be performed as a background treatment and as such is classed as a Non Investigational Medicinal Product (NIMP) for the purpose of this study. Treatment will consist of the infusion of cytotoxic chemotherapy after arterial hepatic angiogram, followed by

	
either selective or super-selective embolization of the arterial vascular bed perfusing the tumour with gelatin/sponge particles. TACE procedure will be standardised across sites and will consist of conventional or drug-eluting beads (DEB) transcatheter superselective arterial chemoembolization utilising doxorubicin at either a fixed dose of 60 mg (for conventional TACE) or a dose ranging from 75-150mg depending on the size of the tumour (for DEB-TACE) followed by tumour vasculature embolization with gelatin sponge particles. TACE is normally administered as a short elective inpatient treatment to allow for monitoring of immediate post-procedural complications. Radiologic follow up after TACE with contrast-enhanced CT or MRI scan will be performed approximately 30 days after TACE as part of SOC prior to IMP administration. Participants who fail to achieve complete tumour devascularisation after the first session of TACE as assessed by follow-up contrast-enhanced scan may be allowed up to 1 further TACE session as per European Association for the Study of the Liver (EASL)/European Organisation for Research and Treatment of Cancer (EORTC) clinical guidelines unless clinical or technical factors preclude repeat treatment. In patients requiring re-treatment, re-screening is not required and time intervals for commencement of IMP and subsequent Dose Limiting Toxicity (DLT) window will remain unchanged.
 
Pembrolizumab. IMP administration will begin no earlier than 30 + 3 days following TACE administration. IMP should be administered on an outpatient basis on Day 1 ± 3 days of each cycle after all procedures/assessments have been completed. Pembrolizumab will be administered at the pre-planned dose as a 30 (-5/+10) minute (min) IV infusion every 3 weeks (Q3W).

--	---

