1.0 INTRODUCTION

1.1 Background

1.1.1 Hepatocellular Carcinoma and trans-arterial chemoembolization.

Hepatocellular carcinoma is the sixth commonest and third most lethal solid malignancy on a global scale[1]. Approximately 60% of patients who are newly diagnosed with HCC do not qualify for curative treatments including liver resection or transplantation[2]. Patients presenting with liver-confined HCC, preserved liver function and performance status cluster into “intermediate stage” or Barcelona Clinic Liver Cancer (BCLC) B stage. In this patient subgroup, where overall survival (OS) often extends beyond 2 years, guidelines recommend TACE with the intent of prolonging OS by achieving local disease control and prevent systemic spread of the disease [3].

The use of TACE in unresectable HCC as a palliative measure to improve survival whilst maintaining quality of life (QOL) is supported by level I evidence stemming from 2 primary randomized controlled trials and subsequent meta-analyses. The efficacy of TACE relies on the dual ischaemic and cytotoxic effect stemming from the sequential intra-arterial delivery of cytotoxic chemotherapy (doxorubicin, epirubicin or cisplatin) followed by direct occlusion of the arterial neo-vascular supply to the tumour. Clinically, this translates into radiologically measured responses in 35% of patients (range, 16%-61%), which correlate with a 14% improvement of patients' survival at 2-years (odds ratio [OR], 0.53; 95% confidence interval [CI], 0.32-0.89; P =.017)[3].

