2.2 Secondary Objective

To determine the efficacy of Pembrolizumab following TACE in participants with intermediate-stage HCC.

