2.6 Tertiary Endpoints

2.6.1 To identify biomarkers of immune response to Pembrolizumab using high-throughput technologies.

Biomarker blood, tissue urine and stool sample collection connected to this study will be established for biomarker research using high throughput proteomic and genomic analysis. Functional characterisation of circulating lymphocyte populations will be performed in parallel. The biomarker biopsy tissue sample taken at screening is optional. Participants will be invited to provide all other additional biomarker blood, urine and stool sample samples for research as well as provide consent for research to be performed on all leftover samples and tissue taken for diagnostic purposes.

2.6.2 To evaluate the efficacy of Pembrolizumab following TACE by improving PFS rates as measured by standard RECIST criteria v 1.1 at pre-defined 12-weekly timepoints.

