3.0 STUDY DESIGN

3.1 Design

The study will be performed at 1-4 sites in the UK and will recruit up to a maximum of 32 evaluable participants. This study is an OL, single arm, sequential phase study evaluating safety, tolerability and preliminary efficacy of sequential TACE followed by Pembrolizumab and will be conducted in two parts.

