6.0 TREATMENT

Treatment will consist of a maximum of 1 year of Pembrolizumab Q3W following TACE.

6.1 TACE.

TACE will be performed as per SOC and will classify as a NIMP for the purpose of this study. Treatment will consist in the infusion of cytotoxic chemotherapy after arterial hepatic angiogram, followed by either selective or super-selective embolization of the arterial vascular bed perfusing the tumour. The procedure will be standardised across sites and will consist of conventional transcatheter arterial chemoembolization (conventional TACE) or drug-eluting beads TACE (DEB TACE) approach. The chemotherapeutic agent of choice will be doxorubicin delivered intra-arterially at the fixed dose of 60 mg for patients who receive conventional TACE. In patients receiving DEB TACE, the dose of doxorubicin will be ranging from 75-150 mg depending on the size of the tumour and according to the standard of care. Doxorubicin should be stored, prepared and disposed of in accordance with the relative Summary of Product Characteristics (SmPC) and hospital procedures. In addition to conventional TACE, drug-eluting beads (DEB) TACE is also considered an acceptable modality for TACE treatment. The local study team site personnel will maintain a dispensing record for each participant. Doxorubicin will be sourced for use in this clinical trial as per normal hospital procedures. Polyvinyl alcohol particles will be the embolizing agent of choice. TACE is normally administered as a short elective inpatient treatment to allow for monitoring of immediate post-procedural complications. Contrast-enhanced CT or MRI scan will be performed approximately 30 days after TACE as part of SOC. Reports will be recorded.

Participants who fail to achieve complete tumour devascularisation after the first session of TACE as assessed

by follow-up contrast-enhanced scan may be allowed up to 1 further TACE session as per EASL/EORTC clinical guidelines unless clinical or technical factors preclude repeat treatment. In participants requiring re-treatment, time intervals for commencement of Pembrolizumab and subsequent DLT window will remain unchanged. No re-screening is required.

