8.3 Primary and Secondary Endpoint Analysis

All participants who receive at least one dose of Pembrolizumab will be included in the safety analysis set.

The frequency of AEs will be assessed for severity (NCI CTCAE v4), expectedness, seriousness and causal relationship to IMP. In addition, AEs will be summarised by toxicity type, impact on IMP and by timing.

All participants who receive at least one dose of Pembrolizumab and undergo disease re-evaluation as per protocol will be included in the efficacy analysis.

Due to sample size constraints, for the primary outcome of assessing the safety and tolerability of Pembrolizumab following TACE and secondary outcomes of ORR every 3 months and QOL, we will use descriptive measures such as frequencies and percentages for categorical variables and means and standard deviations for normally distributed continuous variables, as specified above in section 8.1.

The secondary endpoint of PFSR will be estimated by the Kaplan-Meier method. This rate estimates the proportion of participants who do not progress and are alive at a given time of 12 weekly timepoints. The PFSR is calculated from the start of Imp administration until the date of progression or death from any cause.

Univariate models will be performed for all demographic and other study variables, as statistically appropriate, as well as to test for confounding due to sample size constraints, with models such as Fisher's exact test or the Chi-square test utilised for categorical variables and t-tests or the Wilcoxon test (if the continuous variable does not follow a normal distribution) for continuous ones. For all estimates, 95% confidence intervals will be calculated.

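### The reference scan for tumour response is contradictory and can precede TACE, so ORR may include TACE responses; PFS rates are said to improve with nothing to compare them with

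*Combined protocol and SAP*

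**What the plan says.** **Design.** The Trial Summary gives the trial type as "Open label (OL), Single arm", and section 3.1 says the study "will recruit up to a maximum of 32 evaluable participants". All participants have TACE before the first infusion. A second session may be offered under section 6.1: "Participants who fail to achieve complete tumour devascularisation after the first session of TACE" may be re-treated, without re-screening.

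**Objectives.** The Trial Summary has "To evaluate the efficacy of Pembrolizumab following TACE by improving progression-free survival rates (PFSR" by mRECIST. Its exploratory endpoint and section 2.6.2 repeat the idea for the other criteria: "improving PFS rates as measured by standard RECIST criteria v 1.1". Section 2.2 is more neutral: "To determine the efficacy of Pembrolizumab following TACE in participants with intermediate-stage HCC". Section 2.5 also avoids the word *improving*.

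**Analysis.** Section 8.3 estimates the PFS rate by Kaplan-Meier from the first Pembrolizumab dose. It also names "secondary outcomes of ORR every 3 months and QOL", to be described by frequencies and percentages. It does not say which scan response is measured from.

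**Imaging.** Screening falls in the 28 days before TACE (section 5.1). Trial imaging is at screening and every 12 weeks after that (Table 3, note 2; section 5.1.2.6). A baseline scan need not be repeated if it lies within 35 days of the first dose (sections 1.4.2 and 5.1; Table 3, note 2), or within 35 days of TACE (section 5.1.2.6). A contrast-enhanced scan about 30 days after TACE is standard of care, with reports recorded (section 6.1). No section names it as the response baseline.

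**TACE response.** Section 1.1.1 says of TACE that "this translates into radiologically measured responses in 35% of patients (range, 16%-61"%).

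**The concern.** Response is a change from a reference scan. Here a treatment with known radiological activity is given between screening and the first dose of the drug under study. A pre-TACE reference measures response to the whole sequence. A post-TACE reference comes closer to what happens under Pembrolizumab. The plan lets either be used and does not require the same choice for everyone, so the ORR has no fixed meaning.

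The objective adds to this. To improve a PFS rate there must be a rate to improve on, and the documents give no TACE-alone PFS rate, control or target.

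Two later uses are at stake. Section 8.1 wants preliminary efficacy data to inform a future powered trial. Section 5.1.2.7 will correlate sequencing results with response, in support of the Trial Summary's aim of finding predictive correlates of response to Pembrolizumab. If TACE responses are counted, both uses inherit them.

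**Working it through.** The plan states no efficacy null, target or reference rate, so there is no efficacy figure of its own to reproduce. The check has two parts.

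**1. Which scans can serve as baseline?**

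Inputs: 35-day limit (sections 1.4.2, 5.1, 5.1.2.6; Table 3, note 2); TACE-to-dose interval *d* of 30 to 33 days, or 45 to 48 days if lengthened (section 6.5; Table 3); screening on day -28 to -1 before TACE; standard-of-care scan at about day 30.

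A scan taken *s* days before TACE is *s* + *d* days old at first dose. It meets the first-dose rule only if *s* ≤ 35 − *d*.

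- *d* = 30: *s* ≤ 5 days.
- *d* = 33: *s* ≤ 2 days.
- *d* = 45 to 48: 35 − *d* is −10 to −13, so no pre-TACE scan qualifies.

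A scan from the screening window is 1 + 30 = 31 to 28 + 33 = 61 days old at first dose with the shorter interval, and 1 + 45 = 46 to 28 + 48 = 76 days old with the longer one.

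The day-30 scan is about 0 to 3 days old at first dose with the shorter interval and 15 to 18 days old with the longer one. It meets the first-dose rule in both cases.

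| Rule | Pre-TACE scan | Day-30 post-TACE scan |
|---|---|---|
| First dose, 30 to 33 days | only if taken in the last 2 to 5 days before TACE | qualifies |
| First dose, 45 to 48 days | never | qualifies |
| TACE (section 5.1.2.6) | any scan in the screening window | not excluded by the wording |

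Section 5.1.2.6 does not say on which side of TACE the 35 days run. Since it directly follows the sentence on screening imaging, the natural reading is before TACE. Under that reading, a screening scan acceptable in section 5.1.2.6 usually fails the rule in the other three places. Outside standard of care, no scan is scheduled between screening and the first 12-weekly assessment to replace it.

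A second TACE creates a further case. The day-30 scan that shows incomplete devascularisation precedes the second session, so response measured from it would include the effect of that session.

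**2. What would ORR show with no Pembrolizumab effect?**

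Assumptions: reference scan before TACE, Pembrolizumab adds nothing, the section 1.1.1 TACE response rate *p* applies here, and all 32 are evaluable. Expected responders = 32 × *p*. Intervals are exact (Clopper-Pearson) at the rounded count.

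| TACE response rate | 32 × *p* | Rounded | Observed ORR (95% CI) |
|---|---|---|---|
| 16% | 5.12 | 5/32 | 16% (5% to 33%) |
| 35% | 11.2 | 11/32 | 34% (19% to 53%) |
| 61% | 19.52 | 20/32 | 63% (44% to 79%) |

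For the PFS rate no such calculation is possible. A result of 22/32 = 69% (exact 95% CI 50% to 84%), for example, could not be called better or worse than TACE alone.

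**The case against.** The strongest reply is that this is a safety-first phase Ib. The single arm is openly stated. Section 1.4.2 calls efficacy exploratory, sections 3.1 and 4.1 call it preliminary and describe it for the sequence, and section 8.1 bases the step to phase II on the upper confidence limit for toxicity. ORR appears only as a descriptive item in section 8.3, not among the listed endpoints. Three of the four baseline statements refer to the first dose and mostly exclude a pre-TACE scan.

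Much of that stands, and it rules out several stronger readings.

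- A reader might infer that efficacy would be declared even if Pembrolizumab did nothing. The plan has no efficacy test or success rule, so nothing is declared. Nor is the lack of a control arm an error.
- A reader might set the result against the 8/42 (19%) response quoted for nivolumab in section 1.3.1. At a 35% TACE rate and a pre-TACE baseline, the chance of matching or beating it with 32 participants is 96%. The plan never uses that figure as a benchmark, and at a 16% TACE rate the chance is only 24%.
- A reader might equate complete devascularisation with complete response. The mRECIST appendix is not in the text available, and the argument does not need it.
- A reader might take 16% to 61% as the share with no viable tumour after TACE. Section 1.1.1 reports responses, not clearance.

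The reply does not remove the conflict between section 5.1.2.6 and the other three places, nor the missing statement of the response baseline in section 8.3. Labelling a result exploratory does not settle what it measures.

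**Conclusion.** The concern holds as a defect of definition. The baseline rules contradict each other, permit a reference scan before TACE, and allow the reference to differ between participants and between Parts 1 and 2. Under the screening schedule and the natural reading of section 5.1.2.6, ORR would include TACE responses: about 11 of 32, with a range of about 5 to 20, without any contribution from Pembrolizumab. That size rests on a pre-TACE reference for everyone and on the TACE rate in section 1.1.1 carrying over to this population. If the day-30 scan were used throughout, TACE responses already visible on it would not be counted.

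Separately, the Trial Summary and section 2.6.2 speak of improving PFS rates with no comparator or reference rate. Section 2.2 does not use that word, although it still attributes efficacy to Pembrolizumab alone. The consequence is possible misreading of PFS rate and ORR when planning the later trial and interpreting the biomarker correlations.

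**What to change.** 1. Reconcile sections 1.4.2, 5.1 and 5.1.2.6 and Table 3, note 2, into one baseline rule. State for each scan which side of TACE it falls on and which analysis it serves.
2. In section 8.3, report two response figures:
   - (a) response to the TACE-Pembrolizumab sequence, against the pre-TACE scan and labelled as such;
   - (b) response against the last contrast-enhanced scan after the final TACE session and before the first infusion, read centrally, only in participants with viable measurable disease on that scan.

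   Give separate counts of participants with no viable tumour on that scan and of those with no scan after a second TACE.
3. In the Trial Summary (objective and exploratory endpoint) and section 2.6.2, replace the *improving* wording with: *estimate the 12-weekly PFS rate of the TACE-Pembrolizumab sequence*. State in section 8.3 that neither the PFS rate nor figure (a) isolates the Pembrolizumab effect.
4. Say which response figure the biomarker correlations in section 5.1.2.7 will use.

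Cost: wording changes and one extra table. The post-TACE scan is already standard of care, but section 6.1 only requires its report to be recorded, so the images must be collected and added to the central read. Figure (b) will have a smaller denominator, of a size the documents do not allow one to predict, and a wider interval. No control arm or change in sample size is needed.
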